6.4.4 Reporting of serious adverse events

Investigators and other site personnel must inform the FDA, via a MedWatch/AdEERs form, of any serious or unexpected adverse events that occur in accordance with the reporting obligations of 21 CFR 312.32, and will concurrently forward all such reports to AZ. A copy of the MedWatch/AdEERs report must be faxed to AstraZeneca at the time the event is reported to the FDA. It is the responsibility of the investigator to compile all necessary information and ensure that the FDA receives a report according to the FDA reporting requirement timelines and to ensure that these reports are also submitted to AstraZeneca at the same time.

When reporting to AstraZeneca, a cover page should accompany the MedWatch/AdEERs form indicating the following:

- Investigator Sponsored Study (ISS)

- The investigator IND number assigned by the FDA
- The investigator's name and address
- The trial name/title and AstraZeneca ISS reference number

Investigative site must also indicate, either in the SAE report or the cover page, the causality of events in relation to all study medications and if the SAE is related to disease progression, as determined by the principal investigator.

Send SAE report and accompanying cover page by way of fax to AstraZeneca's designated fax line: [name]

Serious adverse events that do not require expedited reporting to the FDA need to be reported to AstraZeneca preferably using the MedDRA coding language for serious adverse events.

In the case of blinded trials, AstraZeneca will request that the Sponsor either provide a copy of the randomization code/ code break information or unblind those SAEs which require expedited reporting.

All SAEs have to be reported to AstraZeneca, whether or not considered causally related to the investigational product. All SAEs will be documented. The investigator is responsible for informing the IRB and/or the Regulatory Authority of the SAE as per local requirements.

We will submit SAE reports to AstraZeneca using the MedDRA coding language.

6.4.5 **Laboratory safety assessment**

All laboratory equipment and devices will be regularly evaluated by the site and/or outside auditors for Good Clinical Practice and overall laboratory safety.

For the purpose of ensuring compliance with Good Clinical Practice and regulatory agency guidelines, it may be necessary for the Sponsor or a regulatory agency to conduct a site audit or an inspection.

| For blood volume see Section [7.17.1](#).

6.5 **Physical examination**

The physicians at the three sites will perform a general physical examination of all major organ systems.

6.5.1 **ECG**

6.5.1.1 **Resting 12-lead ECG**

A 12-lead resting electrocardiogram will be performed at screening and end of trial.

6.5.1.2 Real time display (telemetry)

Not applicable.

6.5.2 Vital signs

Vital signs will be obtained in the sitting position after five (5) minutes of rest, prior to the viscosity test, and recorded on the CRF.

6.5.2.1 Pulse and blood pressure

Radial pulse will be measured as beats/minute. The quality of the pulse will also be noted. Systolic and diastolic blood pressure will be measured as mmHg.

6.5.2.2 Body temperature

Body temperature will be measured as °F.

6.5.3 Other safety assessments

Pulse volume recordings will be simultaneously obtained at the level of the ankle, metatarsal and toe bilaterally (Parks Flolab, Parks Medical Electronics, Aloha, OR) according to standard protocol

Continuous-wave Doppler will be used to determine ankle-brachial indices as well as toe-brachial indices.

Perimed, Incs laser doppler monitoring system (PeriFlux System 5000, Perimed AB, Sweden) will measure the total local microcirculatory blood perfusion including the perfusion in capillaries, arterioles, venules and shunting vessels. The technique is based on the emission of a beam of laser light carried by a fiber-optic probe. This probe will be connected to a computer system where we will be able to obtain the measurements. This assessment will take only 2-6 min and will not involve the use of any radiation. The measurements of the flow will be performed with and without Valsalva maneuvers.

Perimed's Periflux system has been used in other clinical trials as evidenced in published scientific journals.

6.6 Patient reported outcomes (PRO)

Not applicable.

6.6.1 PRO method or questionnaire

MedDRA.

6.7 Pharmacokinetics

Not applicable.

6.7.1 Collection of samples

Blood samples will be collected with a standard venipuncture. Approximately 3 cc of blood will be collected into an EDTA containing vacutainer (Becton, Dickinson and Company, Franklin Lakes, NJ, USA) and utilized within the Hemathix SCV-200 automated scanning capillary tube viscometer. An additional 20 cc of blood will be collected for CBC and other lab testing.

6.7.2 Determination of drug concentration

Not applicable.

6.8 Pharmacodynamics

Not applicable.

6.8.1 Collection of pharmacodynamic markers

Not applicable.

6.9 Pharmacogenetics

6.9.1 Collection of pharmacogenetic samples

6.10 Some of the laboratory samples will be stored in a -70°C freezer for future assessments and genetic testing if consented by the subject.

Health economics

Not applicable.

7. BIOLOGICAL SAMPLING PROCEDURES

7.1 Volume of blood

Blood samples will be collected with a standard venipuncture. Approximately 3 cc of blood will be collected into an EDTA containing vacutainer (Becton, Dickinson and Company, Franklin Lakes, NJ, USA) and utilized within the Hemathix SCV-200 automated scanning capillary tube viscometer. An additional 20 cc of blood will be collected for CBC testing, fibrinogen, serum chemistry and lipid profiles. A serum pregnancy test will be performed on all women who agree to participate in the trial.

7.2 Handling, storage and destruction of biological samples

7.2.1 Pharmacokinetic and/or pharmacodynamic samples

Not applicable.

7.2.2 Pharmacogenetic samples

Some of the laboratory samples will be stored in a -70°C freezer for future assessments and genetic testing if consented by the subject. For subjects that do not consent for pharmacogenetic, samples would not be collected and/or will be destroyed immediately.

7.3 Labeling and shipment of biohazard samples

Three preprinted labels containing the Subject ID number will be prepared for each subject. The labels will be affixed to the blood specimen tubes for each test as well as each subject's CRF. Blood will be sent to a designated laboratory facility.

7.4 Chain of custody of biological samples

The chain of custody for biological samples follows from the study coordinator and local principal investigator, to the central laboratory facility for blood viscosity or to the site medical center laboratory for all other laboratory assessments.

7.5 Withdrawal of informed consent for donated biological samples

In the event that a subject withdraws his or her informed consent for donated biological samples, all of his or her samples will be disposed of and excluded from further study.

8. ETHICAL AND REGULATORY REQUIREMENTS

8.1 Ethical conduct of the study

The study will be conducted in compliance with the protocol and GCP. In reference to other applicable regulatory requirements, the automated scanning capillary viscometer is an investigational device that requires a minimally invasive sampling procedure that presents no significant risk. It does not by design or intention introduce energy into a subject, and it is not used as a diagnostic procedure without confirmation of the diagnosis by another medically established product or procedure. In addition, the blood sample required for testing in the device will be collected with a standard venipuncture, which is an approved FDA procedure (the blood is not returned to the subject's body). The device is considered to be exempt from IDE regulation in accordance with the provisions specified in 21 CFR 812.2 and 812.5

8.2 Ethics and regulatory review

The Principal Investigator must submit this protocol to an Ethics Review Committee or a similar body (IRB, CCPRB, etc.), and he/she is required to forward a copy of the written approval/advice signed by the Chairman to the Sponsor.

On the approval/advice sheet, the study (title, protocol number, and version), the documents studied (protocol, informed consent material, advertisement, when applicable), and the date of the review should be clearly stated.

Study device supplies will not be released, and the study will not start until a copy of this written approval/advice has been received by the Sponsor.

Complementary information and/or requirements will be described in an appendix, where applicable.

8.3 Informed consent

It is the responsibility of the Principal Investigator to obtain informed consent in compliance with national requirements from each subject prior to entering the study or, where relevant, prior to evaluating the subject's suitability for the study.

The informed consent document used by the Principal Investigator for obtaining subject's informed consent must be reviewed and approved by the Sponsor prior to Ethics Review committee or similar body (IRB, CCRPRB, etc.) submission.

Specific national requirements or specific conditions associated to the study procedures will be described in an appendix, where applicable.

8.4 Changes to the protocol and informed consent form

It is specified that the appendices attached and referred to in the main text of this protocol form an integral part of the protocol.

No change or amendment to this protocol may be made by the Principal Investigator or by the Sponsor after the protocol has been agreed to and signed by both parties unless such change or amendment has been fully discussed and agreed upon by the Principal Investigator and the Sponsor. Any changes so agreed upon will be recorded in writing, and the written amendment will be signed by both the Principal Investigator and Sponsor. The signed amendment will then be appended to this protocol.

Approval/advice of amendments by the Ethics Review Committee or similar body (IRB, CCRPRB, etc.) is then required prior to their implementation, unless there are overriding safety reasons.

If the change or deviation increases risk to the study population, or adversely affects the validity of the clinical investigation or the subject's rights, full Ethics Review Committee approval/advice must be obtained prior to implementation. For changes that do not involve increased risk or affect the validity of the investigation or the subject's rights, such approval/advice may be obtained by expedited review, where applicable.

In some instances, an amendment may require a change to a consent form. The Principal Investigator must receive Ethics Review Committee approval/advice of the revised consent form prior to implementation of the change. In addition, changes to the CRFs, if required, will be incorporated into the amendment.

Prior to initiating the change, the protocol amendment must be submitted to the Regulatory Agencies, where applicable, except under emergency conditions.

8.5 Audits and inspections

By signing this protocol, the Principal Investigator agrees to allow Sponsor Clinical Research/Quality Assurance auditors and regulatory agencies to have direct access to his/her study records for review. These personnel, bound by professional secrecy, will not disclose any personal identity or personal medical information.

These audits involve review of source documents supporting the adequacy and accuracy of data gathered in the Case Report Forms, review of documentation required to be maintained, and checks on drug/device accountability.

9. STUDY MANAGEMENT

9.1 Training of study site personnel

Training of study site personnel is the responsibility of the PI. Training of staff personnel in all amendments should be documented in the Regulatory Binder.

9.2 Monitoring of the study

9.2.1 Source data

According to the guidelines on GCP, the monitor has to check the CRF entries against the source documents. The consent form will include a statement by which the subjects allow the Sponsor's duly authorized personnel (Study Monitoring team) to have direct access to source data which supports data on the CRFs (e.g. subject's medical file, appointment books, original laboratory records, etc.). These personnel, bound by professional secrecy, will not disclose any personal identity or personal medical information.

9.3 Study timetable and end of study

See section 3.1 for complete study timetable and flow chart. The study will conclude at week 16 after the final collection of patient data and laboratory assessments.

10. DATA MANAGEMENT

All local legal requirements regarding the protection of personal data will be adhered to. Patient data will be coded with a subject ID.

All subject data is confidential, but may be subject to review by authorized representatives of the sponsor, independent auditors, IRB, and/or regulatory authorities.

All data will be secured in secure locked cabinets, and on a secure, password-protected server.

11. EVALUATION AND CALCULATION OF VARIABLES

11.1 Calculation or derivation of efficacy variable(s)

Blood samples will be collected with a standard venipuncture. Approximately 3 cc of blood will be collected into an EDTA containing vacutainer (Becton, Dickinson and Company, Franklin Lakes, NJ, USA) and utilized within the Hemathix SCV-200 automated scanning capillary tube viscometer. An additional 5 cc of blood will be collected for CBC testing.

Pulse volume recordings will be simultaneously obtained at the level of the ankle, metatarsal and toe bilaterally (Parks Flolab, Parks Medical Electronics, Aloha, OR) according to standard protocol

Continuous-wave Doppler will be used to determine ankle-brachial indices as well as toe-brachial indices.

11.2 Calculation or derivation of safety variable(s)

Not applicable.

11.2.1 Other significant adverse events (OAE)

Not applicable.

11.3 Calculation or derivation of patient reported outcome variables

Not applicable.

11.4 Calculation or derivation of pharmacokinetic variables

Not applicable.

11.5 Calculation or derivation of pharmacodynamic variable(s)

Not applicable.

11.5.1 Calculation or derivation of the relationship between pharmacokinetic and pharmacodynamic variables

Not applicable.

11.5.2 Population analysis of pharmacokinetic/pharmacodynamic variables

Not applicable.

11.6 Calculation or derivation of pharmacogenetic variables

Not applicable.

11.7 Calculation or derivation of health economic variables

Not applicable.

12. STATISTICAL METHODS AND SAMPLE SIZE DETERMINATION

12.1 Description of analysis sets

The data will be analyzed within the crossover design framework using repeated measures ANOVA. The analyses of treatment effect, period effect, and sequence effect will be performed at the 0.05 significance level.

12.1.1 Efficacy analysis set

For the first primary aim, a pre-planned contrast statement (proc mixed) will be used to compare the pooled effect of aspirin-ticagrelor with aspirin. Similarly, for the second primary aim, a contrast statement will be used to compare the pooled effect of ticagrelor monotherapy with aspirin. A one-tailed hypothesis test will be used for each contrast, and a Bonferroni correction will be used to control family wise error rate; a one-tailed significance level of 0.025 will be used for both contrasts. The above contrasts shall act effectively as a paired t-test on the dependent variable blood viscosity.

For the first secondary aim, an effect size will be calculated to estimate the standardized difference between ticagrelor monotherapy and combination aspirin-ticagrelor. Low-dose aspirin was previously reported to have no significant effect on blood viscosity. The present study is powered to detect differences between ticagrelor and low-dose aspirin—not between ticagrelor monotherapy and combination aspirin-ticagrelor. An effect size corresponding to a dependent t-test will be calculated to determine the practical magnitude of the difference in blood viscosity measures between the two ticagrelor arms of the study.

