2. STUDY OBJECTIVES

2.1 Primary objective

- (1) Compare the effect of aspirin-ticagrelor with aspirin in a double blind, randomized, cross-over study design (weeks 1-4, weeks 6-10, and weeks 12-16) on blood viscosity at both low (5 s^{-1}) and high (300 s^{-1}) shear rates at the end of each 4-week treatment period.
- (2) Compare the effect of ticagrelor monotherapy with aspirin in a double blind, randomized, cross-over study design (weeks 1-4, weeks 6-10, and weeks 12-16) on blood viscosity at both low (5 s^{-1}) and high (300 s^{-1}) at the end of each 4-week treatment.

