6.3 Efficacy

6.3.1 Whole Blood Viscosity

Blood samples will be collected with a standard venipuncture. Approximately 3 cc of blood will be collected into an EDTA-containing vacutainer (Becton, Dickinson and Company, Franklin Lakes, NJ, USA) and transported in a refrigerated shipment kit to Rheovector LLC (Camden, NJ) for viscosity testing. Blood viscosity will be measured using an automated scanning capillary tube viscometer across a physiologic range of shear rates of 1-1000 s⁻¹ in increments of 0.1 s⁻¹. Blood viscosity levels at 5 s⁻¹ will be reported as low-shear viscosity,

and blood viscosity measurements at 300 s^{-1} will be reported as high-shear viscosity. An additional 5 cc of blood will be collected for CBC testing.

Pulse volume recordings will be simultaneously obtained at the level of the ankle, metatarsal and toe bilaterally (Parks Flolab, Parks Medical Electronics, Aloha, OR) according to standard protocol

Continuous-wave doppler will be used to determine ankle-brachial indices or toe-brachial indices, and flow velocity profiles.

Perimed Inc's laser flow doppler system will be used to determine microcirculatory flow in a private research subject room. Perimed staff will train and certify study members. Only trained and certified study members listed on the protocol will be permitted to perform the procedure on study subjects.

The Principal Investigator is responsible for ensuring that all staff involved in the study is familiar with the content of this section.

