12.3 Determination of sample size

The scanning capillary viscometer that will be used in the proposed study was employed in an earlier study of 47 patients with hyperhomocysteinemia in addition to stable CVD or high CVD risk factors based on a Framingham score of >20% [13]. In this prior CVD population, mean blood viscosity levels at a low shear rate of 5 s^{-1} were reported to be $9.98 \pm 2.42\text{ cP}$ in the control group at baseline. A standard deviation of 2.42 cP for low-shear (5 s^{-1}) blood viscosity was used throughout our sample size calculations. Separately, treatment by clopidogrel 75 mg daily for 3 weeks was reported to reduce viscosity levels by 0.6 cP and 5.0 cP at shear rates of 94.5 s^{-1} and 0.94 s^{-1} , respectively [12]. Using this data, blood viscosity reduction of 2.0 cP by clopidogrel was interpolated for a shear rate of 5 s^{-1} . The present cross-over design study is powered to detect a 2.0 cP difference in low-shear blood viscosity at a shear rate of 5 s^{-1} , relative to aspirin 81 mg, with 90% power using a type I error rate of 5%. Combination aspirin-ticagrelor and low-dose aspirin control will be compared, and separately, ticagrelor monotherapy and low-dose aspirin control will be compared. This requires 72 patients (24 patients in each of 3 groups). Accounting for dropout, we will randomize 90 patients, or 30 patients in each of 3 arms. The effects of combination aspirin-ticagrelor and ticagrelor monotherapy will also be compared as a secondary aim.

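### The Bonferroni correction counts two treatment contrasts, but the primary objectives need four tests (two contrasts at two shear rates), so one-tailed 0.025 per test does not hold the family-wise error at 5%

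*Combined protocol and SAP*

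**What the plan says.** Section 2.1 (Primary objective) lists two comparisons. The first, aspirin-ticagrelor against aspirin, is made "on blood viscosity at both low (5 s^{-1}) and high (300 s^{-1}) shear rates". The second, ticagrelor alone against aspirin, is likewise made "on blood viscosity at both low (5 s^{-1}) and high (300 s^{-1}) at the end of each 4-week treatment".

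Section 6.3.1 treats the two shear rates as separate variables. The value at 5 s⁻¹ is the low-shear viscosity, "and blood viscosity measurements at 300 s^{-1} will be reported as high-shear viscosity".

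Section 12.1.1 (Efficacy analysis set) plans one contrast per primary aim. On sidedness: "A one-tailed hypothesis test will be used for each contrast". On multiplicity: "a Bonferroni correction will be used to control family wise error rate; a one-tailed significance level of 0.025 will be used for both contrasts". On the outcome: "The above contrasts shall act effectively as a paired t-test on the dependent variable blood viscosity". It gives no shear rate.

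Section 12.3 uses a type I error rate of 5% and 90% power, for low shear only: "The present cross-over design study is powered to detect a 2.0 cP difference in low-shear blood viscosity".

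**The concern.** Two regimens compared with aspirin at two shear rates make four primary hypotheses. The divisor in Section 12.1.1 is two, which is the number of treatment contrasts. The correction is there to control the family-wise error, yet it leaves the second shear rate out of the count.

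The plan has no rule for combining the shear rates. A significant result at either one, for either regimen, could therefore be presented as a primary success, and which shear rate decides the matter could be settled after the results are known. The chance of at least one false primary claim would then be larger than the plan intends.

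**Working it through.** **Inputs**
- Primary tests: 2 contrasts × 2 shear rates = 4 (Section 2.1; separate variables in Section 6.3.1).
- Level per test: one-tailed 0.025 (Section 12.1.1).
- Family-wise target: 5%. Section 12.1.1 does not state it. It follows from 2 × 0.025 = 0.05 and agrees with the 5% in Section 12.3.
- Correlation between the two contrasts: 0.5 (assumption). Both contrasts subtract the same aspirin period. If the three periods have equal error variance σ² and independent errors, each contrast has variance 2σ² and their covariance is σ², so the correlation is σ²/2σ² = 0.5.
- Correlation between low-shear and high-shear results: not in the documents, so a range from 0 to 1 is shown.

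**The plan's own figure**

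0.05 / 2 = 0.025, which reproduces the stated level. For two tests:
- Bonferroni bound: 2 × 0.025 = 5%
- if independent: 1 − 0.975² = 4.94%
- with correlation 0.5: 4.5%

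The correction is therefore adequate for one shear rate taken alone.

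**Four tests at 0.025**
- Bonferroni bound: 4 × 0.025 = 10%
- if independent: 1 − 0.975⁴ = 9.63%

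For correlated tests, 8 million draws were simulated from a four-variate normal distribution with no true effect anywhere. The correlation matrix was the Kronecker product of the shear-rate matrix and the contrast matrix (0.5). The table gives the probability that at least one of the four statistics exceeds the one-tailed critical value.

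| Correlation between shear rates | Four tests at 0.025 | Four tests at 0.0125 | Claim only if both shear rates are significant at 0.025 |
|---|---|---|---|
| 0 | 8.9% | 4.6% | 0.1% |
| 0.3 | 8.5% | 4.5% | 0.5% |
| 0.5 | 8.1% | 4.3% | 0.9% |
| 0.7 | 7.4% | 4.0% | 1.6% |
| 0.9 | 6.3% | 3.3% | 2.8% |
| 1.0 | 4.5% | 2.3% | 4.5% |

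Among the values examined, the error at 0.025 is below 5% only at a correlation of 1.0, where the two shear rates are the same test.

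**The proposed order of testing**

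Within each contrast, 5 s⁻¹ is tested at 0.025, and 300 s⁻¹ is tested at 0.025 only after a significant low-shear result. Each two-step sequence has an error of at most 0.025, so the two together have at most 2 × 0.025 = 5%. When no effect exists, any false claim must begin with a false low-shear result, so the error is that of the two low-shear contrasts: 4.5% at correlation 0.5.

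**The case against.** The strongest reply is that the plan leaves the decision rule open and does not actually say that either shear rate suffices. Two other readings would make 0.025 enough.

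- **Low shear is the real primary.** Section 12.3 powers the study on 5 s⁻¹ alone, and Section 12.1.1 speaks of one dependent variable. But Section 2.1 gives the two shear rates equal primary standing, and nothing ranks them. This reading is a good reason to write the ranking down; it does not show that the plan already has one.
- **Both shear rates must succeed.** This removes the inflation (last column of the table), but the plan never requires it. If it were the rule, the 90% power in Section 12.3 would not be the power of the claim. Power for success at both shear rates cannot exceed that at low shear, and it cannot be computed, because no effect size or standard deviation is given for 300 s⁻¹.

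Section 1.2 hypothesises that both regimens are superior to aspirin. If only that joint claim counted, accepting either shear rate would still keep the error within 5%. However, a Bonferroni correction over the contrasts makes sense only if each regimen can be claimed by itself.

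Two points limit the size. First, the tabulated figures assume no effect anywhere. With three true null hypotheses the bound is 3 × 0.025 = 7.5%. With two it is 5%, so there is no excess if both regimens truly lower low-shear viscosity. Second, both values come from one sample and one viscometer scan, so zero correlation is an extreme case. These points bear on how large the excess is. Family-wise control has to cover the case of no effect as well.

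**Conclusion.** The concern holds. The plan sets out to control the family-wise error, lists four primary tests, and corrects for two. If success at either shear rate counts, which nothing in the plan rules out, the error is about 6% to 9% against an implied 5%, with a ceiling of 10%.

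The direction is certain for any shear-rate correlation up to 0.9 under the stated assumptions. The exact size is not known, because it rests on an assumed 0.5 between contrasts, an undocumented correlation between shear rates, and the absence of any true effect. The low-shear comparison taken alone is correctly controlled. Because the gap concerns the error rate of the primary claim and cannot be credibly closed once results are known, it must be fixed before unblinding.

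**What to change.** In Section 2.1, name viscosity at 5 s⁻¹ at the end of each treatment period as the primary endpoint. In Section 12.1.1:
- Test each of the two low-shear contrasts at one-tailed 0.025.
- For each contrast separately, test 300 s⁻¹ at one-tailed 0.025 only if that contrast is significant at 5 s⁻¹.
- State the 5% family-wise target.

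This takes a few sentences. The sample size and the power of the low-shear tests do not change. The drawback is that a high-shear result cannot be claimed as primary for a regimen whose low-shear result fails.

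If the sponsor wants the two shear rates to remain equal, the alternative is 0.05 / 4 = 0.0125 per test. At low shear this costs little. With 72 completers, a 2.0 cP difference and zero within-patient correlation (SD of differences 2.42 × √2 = 3.42 cP), power in a paired analysis moves from 99.8% to 99.6%. Power at 300 s⁻¹ stays unknown under either option until an effect size and standard deviation are supplied.

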1.2 Research hypothesis

Both aspirin-ticagrelor and ticagrelor monotherapy will be superior to aspirin monotherapy in the reduction of whole blood viscosity at the end of each 4 week treatment period.

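### Holm step-down in place of single-step Bonferroni for the two primary contrasts would keep the same family-wise error and never reject less, but the gain is negligible at the planned effect and sample size

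*Combined protocol and SAP*

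**What the plan says.** Section 1.2 hypothesises, for the close of every treatment period, that "Both aspirin-ticagrelor and ticagrelor monotherapy will be superior to aspirin monotherapy in the reduction of whole blood viscosity". Section 2.1 lists the two comparisons with aspirin as separate numbered primary objectives, each at low (5 s^-1) and high (300 s^-1) shear.

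Section 12.1.1 gives the testing rule. Both contrasts are tested one-tailed. For multiplicity the rule reads: "a Bonferroni correction will be used to control family wise error rate; a one-tailed significance level of 0.025 will be used for both contrasts". Two tests at 0.025 make a one-tailed family-wise level of 0.05. No step-down or ordering rule appears there or elsewhere in section 12. The same section says that the contrasts act as paired t-tests.

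Section 12.3 says that the trial is "powered to detect a 2.0 cP difference in low-shear blood viscosity" at 5 s^-1, "with 90% power using a type I error rate of 5" percent, with an SD of 2.42 cP and 72 patients (90 randomized to allow for dropout). It does not say whether the 5% is one- or two-sided, whether it is before or after the Bonferroni split, or what the power is for showing both regimens superior.

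**The concern.** Under single-step Bonferroni the second contrast must still pass one-tailed 0.025 after the first has been rejected. This is stricter than a 5% family-wise error requires. Once one of two null hypotheses is rejected, only one remains, and Holm allows it the full 0.05.

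Take one-tailed p-values of 0.01 and 0.04 in a two-test family. Bonferroni claims one regimen. Holm claims both, with the family-wise error still at most 5%. What is at stake is some power for the joint statement in section 1.2, given up with no error control in return. The question is how much.

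**Working it through.** **Inputs.** From 12.3: effect 2.0 cP, SD 2.42 cP, 72 completers, 90% power, type I error 5%. From 12.1.1: one-tailed 0.025 per contrast, paired analysis. Not in the documents: the within-patient correlation r, so a range is shown, and the correlation between the two contrasts.

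**Correlation between contrasts.** Assume equal variances and the same r for every pair of treatments. Each difference from aspirin then has variance 2σ²(1−r), and the two differences have covariance σ²(1−r). Their correlation is 0.5 whatever r is.

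**The plan's own sample size.** As two parallel groups at one-tailed 0.05:

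n per group = 2 × 2.42² × (1.645 + 1.282)² / 2.0² = 25.1, so 26.

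The plan has 24, where power is Φ(2.0 / (2.42 × √(2/24)) − 1.645) = Φ(1.218) = 88.8%. This is close to the stated 90%, although three groups of 26 make 78, not 72. At one-tailed 0.025 the same formula gives 31 per group, and 81.7% power at 24. Of the variants tried, only the unadjusted one-tailed 0.05 calculation comes near 24 per group.

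**Error control.** With both nulls true, Holm and Bonferroni have the same family-wise error: 4.5% at contrast correlation 0.5 and 4.9% at 0. With one null true, simulation at contrast correlation 0.5 gives 4.96% to 4.99% for Holm. Both stay within 5%. Holm's bound holds under any correlation.

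**Power to show both.** Let Z1 and Z2 be bivariate normal with common mean d and correlation 0.5.

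- Bonferroni: P(both > 1.960).
- Holm: P(both > 1.645) − P(both between 1.645 and 1.960).
- d = effect / SE, with SE = 2.42 × √(2(1−r)/72), which is 0.403 at r = 0, 0.349 at r = 0.25 and 0.285 at r = 0.5.

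| True effect (cP) | r | d | Bonferroni, both | Holm, both |
|---|---|---|---|---|
| 2.0 | 0 | 4.96 | 99.7% | 99.9% |
| 2.0 | 0.25 | 5.73 | 99.98% | 99.995% |
| 1.5 | 0 | 3.72 | 93.0% | 96.4% |
| 1.5 | 0.25 | 4.29 | 98.2% | 99.2% |
| 1.0 | 0 | 2.48 | 55% | 67% |
| 1.0 | 0.5 | 3.51 | 89% | 94% |

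These use a normal approximation and ignore the degrees of freedom spent on period and sequence.

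**At a nominal 90% per contrast, ignoring the planned N.** If the 90% is at one-tailed 0.025, d = 1.960 + 1.282 = 3.242. Showing both is then 83.2% with Bonferroni and 89.9% with Holm. With contrast correlation 0 the pair is 81.0% and 89.1%; with 0.9 it is 86.9% and 91.4%. If the 90% is at one-tailed 0.05, d = 1.645 + 1.282 = 2.926, and the pair is 73.3% and 82.5% at contrast correlation 0.5.

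**The case against.** The strongest reply is that nothing in the plan is wrong. Bonferroni at 0.025 is valid, pre-specified and internally consistent, and preferring Holm is a matter of efficiency. That stands.

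A reader might infer that the trial forgoes about seven points of power, 83% to 90%. The documents do not support this. The pair needs 90% power at one-tailed 0.025, which 12.3 does not say, and it describes a smaller trial than the one planned. In the planned paired analysis 72 completers already give at least 99.7% at 2.0 cP.

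A reader might also infer that the trial succeeds only if both contrasts succeed. Section 1.2 is worded that way, but no section sets it as a success rule. Section 2.1 numbers the objectives separately and 12.3 treats the comparisons separately. If both were required, no correction would be needed at all: each contrast could be tested at one-tailed 0.05, giving 90.4% against Holm's 89.9% in the nominal-90% case with contrast correlation 0.5. Holm is the improvement for the plan as written, with two separate claims under family-wise control.

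Two further limits stand. First, one-tailed 0.025 corresponds to two-sided 0.05. Under Holm the second regimen could be claimed at one-tailed 0.05, a weaker standard than the first. Second, 2.1 puts high shear in both primary objectives. With four tests Holm's levels are 0.0125, 0.0167, 0.025 and 0.05, and a p-value of 0.04 passes only if it is the largest and the other three have passed. The p = 0.01 and 0.04 example is therefore only for a two-test family.

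In the other direction, 2.0 cP is not a ticagrelor result. Section 12.3 interpolates it from clopidogrel data at two other shear rates. A smaller true effect is plausible enough to plan for, and there Holm helps.

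**Conclusion.** The point holds as a cheap improvement, not as a fault in the plan. For the two contrasts in 12.1.1, Holm has the same one-tailed 5% family-wise control and never rejects less. This needs no assumption about effect, SD or correlation.

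The size does depend on assumptions. At the planning values the gain is 0.2 points or less for any non-negative within-patient correlation. It grows to about 3 points at 1.5 cP (r = 0), and at 1.0 cP to about 12 points (r = 0) or 5 points (r = 0.5). The 1.5 and 1.0 cP effects and the values of r are illustrative. The contrast correlation of 0.5 follows from equal variances and equal within-patient correlations, which the plan does not state.

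**What to change.** In 12.1.1, replace the Bonferroni sentence by Holm step-down at one-tailed family-wise 0.05: test the smaller p-value at 0.025 and, only if it is significant, the larger at 0.05. State whether high shear belongs to the primary family; if it does, apply Holm across all four tests. In 12.3, say at which level the 90% applies and give the power for showing both regimens superior.

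The change costs a few sentences, with no patients and no data, and must be fixed before unblinding. The plan should state the two downsides: the second contrast may be claimed while its ordinary two-sided 95% interval includes zero, and simultaneous intervals that match Holm are less simple than Bonferroni intervals. Reporting unadjusted intervals beside the Holm decision is a workable answer.
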